**Type of Investigation:**

Double-blinded Randomized Crossover Trial

**Objectives of the Investigation:**

The study will examine whether inhibition of the pre-supplementary motor area (pSMA) using transcranial magnetic stimulation (TMS) normalizes activity in pSMA-connected circuits, improves response inhibition, and reduces compulsions in adolescents with OCD.

**Participants:**

The participants for this study will consist of 14 youth ages 13-18 years with OCD.

**Duration of the Investigation:**

Length of the study is one year. Duration of the study for individual participants will be 3-4 weeks.

**Study Design:**

We will use a within-subject, counterbalanced design comparing TMS vs Sham in a brief 2-visit protocol enrolling 14 youth (age 13-18) with OCD. At each visit, youth will complete the Stop Signal Task (SST) with concurrent electroencephalogram (EEG) pre- and post- TMS or Sham. TMS will be delivered over pSMA using continuous TBS (cTBS). After each visit, youth will rate symptoms using ecological momentary assessment (EMA).

**Study Procedures:**

Overall, study procedures include (a) pre-screening for initial eligibility determination; (b) clinical interview for final eligibility determination, (c) two study visits at which youth will receive TMS or Sham and complete EEG and SST procedures. Assessment procedures include structured diagnostic interviews, and safety screening for TMS. Interested participants will complete a brief phone screen and provide medical records for review before scheduling a clinical interview. Clinical Interview: Participants will complete informed consent (signature required from one parent/guardian), child assent, and assessment of inclusion/exclusion criteria (Mini Kid, CYBOCS, TMS screen; see Measures). Interviews will be administered by the RA, who is already employed at PARC and trained to a reliable standard on all measures. At each of visits 1 and 2, participants will complete a TMS safety screen and medication tracking form; they will then complete the SST with concurrent EEG pre- and post- TMS or Sham. The AEQ will be completed at the end of each visit. Between visits, youth will rate symptoms using EMA (see Measures). Visits 1 and 2 will occur at least one week apart to ensure that any acute TMS effects are no longer active by visit 2. Single session rTMS aftereffects on EEG suggests aftereffect durations <70 min.

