**Inclusion Criteria:**

[figure not shown]
- Age 13-18 years
- Presence of OCD, as indicated by score on the Children's Yale-Brown Obsessive-Compulsive Scale
- Patient and one parent speak English fluently (to ensure comprehension of study measures and instructions)
- Right-handed
- If taking psychotropic medications, these have been stable for  $\geq$  6 weeks and are expected to remain stable for the approximately 3-week study protocol
- If currently in psychotherapy, symptom improvement has plateaued (no improvement in the past 6 weeks and symptoms expected to remain stable for the approximately 3-week study protocol)

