#### Study Design Flow Chart:

#### Study Assessment Measures:

- 1) Mini-Kid; the Mini-Kid 7.0 is a brief, structured interview measuring psychiatric diagnoses in children according to DSM-V and ICD-10 criteria.
- 2) CY-BOCS, is the “gold standard” clinical interview for assessment of OCD symptoms.
- 3) Screening Questionnaire for TMS Candidates; screens for TMS contraindications and will be administered in an interview format with both the child and parent present.
- 4) TMS Adverse Effects Questionnaire (AEQ) is a 13-item questionnaire completed by patient (items 1-10) and clinician (items 11-13).
- 5) The SST is a well-validated computerized task measuring RI. The SST is a visual choice reaction time task in which participants watch arrows (left or right) on the screen and respond by pressing the appropriate button. In a randomly assigned proportion of trials, an audible signal is heard after presentation of the arrow, and subjects are instructed to inhibit the motor response (button press). The inter-stimulus interval and stop-signal delay are varied according to individual performance so that each person can successfully inhibit responses to 50% of stop trials. SSRT (time required to inhibit a prepotent motor response) is calculated from these data. Successful stop trials (i.e., those in which a motor response is successfully inhibited) are most relevant for understanding functional neural correlates of RI, and will be of primary interest in EEG analyses (see below).
- 6) EMA will be used to obtain youth ratings on three items (modified from NIMH rating scales) assessing obsessions, compulsions, and mood on a 7-point scale (1 = not at all to 7 = very much). These items have shown differential change with frequent assessment post-TMS for adults with OCD and have been used in EMA studies of OCD. Youth will receive a text message prompt every two hours (between 9am and 9pm) over the two days following the clinical interview and each study visit (6 days total). The text prompt will include a redcap link for completing EMA items. Similar EMA items and procedures have been used successfully with adolescents of diverse backgrounds in a large number of studies to date.

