#### **Randomization:**

The order in which participants receive TMS and Sham (visit 1 or 2) will be randomly assigned (blocking on medication status, biological sex, and baseline CYBOCS severity) and masked for all study staff except for the statistician.

[figure not shown]

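### EMA-rated compulsions (Aim 3, hypothesis 2): nothing keeps the post-TMS and post-Sham EMA days on the same weekdays, which adds avoidable noise to the contrast

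*Combined protocol and SAP*

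**What the plan says.** Study Procedures sets a minimum gap only: "Visits 1 and 2 will occur at least one week apart". The reason given is washout: "to ensure that any acute TMS effects are no longer active by visit 2". Neither there nor elsewhere in the available text is the weekday of the two visits fixed or matched. The Study Design Flow Chart is not reproduced in that text and might carry scheduling detail.

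Under Study Assessment Measures, item 6, EMA runs "over the two days following the clinical interview and each study visit (6 days total"). Its clock times are standard on every EMA day: "Youth will receive a text message prompt every two hours (between 9am and 9pm").

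Under Randomization, the order of TMS and Sham "will be randomly assigned (blocking on medication status, biological sex, and baseline CYBOCS severity"). No calendar factor is used. For the task and EEG, Study Procedures says of each visit that "they will then complete the SST with concurrent EEG pre- and post- TMS or Sham".

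The Data Analysis paragraph tests a visit-type by pre/post interaction for P3, SSRT and EMA-rated compulsions, using generalized linear mixed models, and names no day-type term. The Masking section requires the session date to be recorded.

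On duration, the plan says "Duration of the study for individual participants will be 3-4 weeks". The Inclusion Criteria require that medication, and symptoms in those receiving psychotherapy, be "expected to remain stable for the approximately 3-week study protocol".

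**The concern.** In a crossover each youth is their own control, so the two conditions should be measured under like circumstances. A visit on Monday, Tuesday or Wednesday is followed by two weekdays, a Thursday visit by Friday and Saturday, and a Friday visit by a full weekend. Compulsions may plausibly be rated differently on school days and weekends, and different prompts may be answered. If a youth's TMS block falls on school days and the Sham block on a weekend, that difference enters the individual TMS–Sham contrast directly. The plan allows for as few as 10 analysable participants, so it has little precision to spare on this outcome.

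**Working it through.** **1. The plan's own figure.** Sample size and power gives no scheduling figure, but it states 0.8 power at N = 10 for d = 0.51 (correlation .80) and d = .70 (correlation .60). A repeated-measures F test with m = 4 measurements, f = d/2, λ = f²·N·m/(1−ρ) and df 3 and 27 comes close:

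- d = 0.51, ρ = .80: λ = 0.255² × 40 / 0.20 = 13.0; power 0.813.
- d = .70, ρ = .60: λ = 0.35² × 40 / 0.40 = 12.25; power 0.787.

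That statement counts four EEG/SST observations per participant. The correlations it cites are for SSRT and P3, and none is given for EMA. Step 4 therefore sets EMA power at 0.80 with matched days and asks what mismatch costs.

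**2. What cancels and what does not.** For SSRT and P3 the contrast is (post − pre at the TMS visit) − (post − pre at the Sham visit). A shift in level shared by pre and post of one visit drops out. For EMA, the only block before any stimulation follows the clinical interview. If it is the pre measurement for both conditions, the contrast is (post-TMS − interview) − (post-Sham − interview) = post-TMS − post-Sham. The interview block drops out and the day-type difference stays.

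**3. How often the blocks differ.** Assume that both visits fall independently and evenly on Monday to Friday. Let W be the weekend share of a block: 0 with probability 0.6 (Mon–Wed), 0.5 with probability 0.2 (Thu), 1 with probability 0.2 (Fri).

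- P(same share) = 0.36 + 0.04 + 0.04 = 0.44, so P(different) = 0.56.
- E(W) = 0.30; E(W²) = 0.2 × 0.25 + 0.2 × 1 = 0.25; Var(W) = 0.25 − 0.09 = 0.16.
- Var(W₁ − W₂) = 2 × 0.16 = 0.32; SD 0.566.

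With all seven days equally likely, P(different) = 28/49 = 57% and the SD is about 0.52, so excluding weekend visits is not what drives the result.

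**4. What it costs.** Let δ be the weekend effect in SD units of a block mean (assumed). The contrast variance is 2(1−ρ) with matched days and 2(1−ρ) + 0.32δ² without matching. A two-sided paired t test with N = 10 and df = 9 has 0.80 power at a standardised contrast of 0.996. Mismatch divides that contrast by the square root of the variance ratio.

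| ρ | δ | Variance, matched → unmatched | Increase | Power |
|---|---|---|---|---|
| .80 | 0.2 | 0.40 → 0.4128 | 3.2% | 0.788 |
| .80 | 0.3 | 0.40 → 0.4288 | 7.2% | 0.772 |
| .80 | 0.5 | 0.40 → 0.48 | 20% | 0.726 |
| .60 | 0.2 | 0.80 → 0.8128 | 1.6% | 0.794 |
| .60 | 0.3 | 0.80 → 0.8288 | 3.6% | 0.786 |
| .60 | 0.5 | 0.80 → 0.88 | 10% | 0.762 |

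With visits a whole number of weeks apart, W₁ = W₂ and the added term is zero, apart from holidays.

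**5. The two durations.** Participation may last up to 4 weeks, while stability is expected for about 3. A participant can be within the first period and beyond the second.

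**The case against.** Several stronger readings are tempting, and the documents do not support them.

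- A reader might infer that free visit start times spoil the SSRT and P3 contrasts. They do not for a level shift, which cancels (step 2). Only a time-of-day effect on the change itself would remain, and nothing in the documents points to one. EMA clock times are already fixed.
- A reader might infer bias. Order is randomised, so the expected bias is zero. A chance shift in the mean contrast, for example 0.5 × 0.566/√10 = 0.09 SD, is the same added variance seen at group level, not a second harm, and a valid test allows for it.
- A reader might infer that the gap is unbounded, or that a rule of exactly 7 or 14 days would keep both visits inside the stability period. The 3-4 week duration bounds the gap loosely. Fixing the gap between visits leaves the interval from interview to visit 1 open. Medication is also tracked at each visit.

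Three objections to the remaining point carry weight. First, its size rests on assumptions: if families tend to rebook the same weekday, 56% is too high, and outside term the school effect largely disappears. Second, a rigid rule could cost participants. Losing one of 10 completers multiplies the variance of every mean contrast by 10/9, an 11% increase, which exceeds every scenario in the table except δ = 0.5 at ρ = .80. That argues for matching as a target, not a requirement. Third, day type can be recovered from recorded session dates and modelled. This is a sound backup, but with about 10 participants the adjustment is itself imprecise, so preventing the mismatch is better where it can be done.

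**Conclusion.** The point holds as a low-cost improvement in precision for one outcome, EMA-rated compulsions. The visible text lets the post-TMS and post-Sham blocks differ in weekend days, and neither the EMA design nor the stated model removes the difference. Under even, independent Monday-to-Friday booking, 56% of participants would be mismatched. For a weekend effect of 0.2 to 0.5 SD, power falls from 0.80 to about 0.79–0.73 at a correlation of .80 and to about 0.79–0.76 at .60. The weekend effect, the booking pattern and the use of these correlations for EMA are all assumptions. The documents support no claim of expected bias, and no loss for SSRT or P3 from a shift common to pre and post.

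The difference between the participation period and the stability period is a separate, textual matter.

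**What to change.** - **Study Procedures:** keep the one-week minimum and add that visit 2 is booked on the same weekday as visit 1, a whole number of weeks later, wherever possible. State that participants who cannot match are kept in the study and the analysis.
- **Data Analysis, Aim 3 hypothesis 2:** add a weekday/weekend term for each EMA day to the EMA model, derived from the session dates already recorded under Masking. This deals with unmatched pairs.
- **Duration of the Investigation and the eligibility criteria:** reconcile the 3-4 week participation period with the approximately 3-week stability period.

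The cost is slightly less flexible booking and one extra model term. Stimulation and the EMA schedule relative to each visit stay as they are.

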**Inclusion Criteria:**

[figure not shown]
- Age 13-18 years
- Presence of OCD, as indicated by score on the Children's Yale-Brown Obsessive-Compulsive Scale
- Patient and one parent speak English fluently (to ensure comprehension of study measures and instructions)
- Right-handed
- If taking psychotropic medications, these have been stable for  $\geq$  6 weeks and are expected to remain stable for the approximately 3-week study protocol
- If currently in psychotherapy, symptom improvement has plateaued (no improvement in the past 6 weeks and symptoms expected to remain stable for the approximately 3-week study protocol)

**Exclusion Criteria:**

- Medical conditions contraindicated for TMS or EEG, including history of intracranial pathology, increased intracranial pressure, epilepsy or seizures, traumatic brain injury, brain tumor, stroke, implanted medical devices, possible pregnancy (female of childbearing age not using effective contraception), or any other serious medical condition (note that medical history will be reviewed by a study physician prior to TMS administration)
- Metal in the head, except mouth (e.g., cochlear implant, implanted brain stimulators, aneurysm clips)
- Active suicidality or psychosis
- Existing diagnosis of Autism Spectrum Disorder, mental retardation, or cognitive disability
- Substance abuse or dependence
- Taking a stimulant medication (and unwilling to forgo on study visit days)
- Taking medication with the potential to lower seizure threshold (e.g., neuroleptics, antipsychotics)
- Patient is a ward of the state

To increase external validity of findings, we will include participants taking psychotropic medications that have been stable for 6 weeks and expect to remain stable for the approximately 3-week study protocol (with the exception of those taking medications that reduce seizure threshold).

#### Study Design Flow Chart:

#### Study Assessment Measures:

- 1) Mini-Kid; the Mini-Kid 7.0 is a brief, structured interview measuring psychiatric diagnoses in children according to DSM-V and ICD-10 criteria.
- 2) CY-BOCS, is the “gold standard” clinical interview for assessment of OCD symptoms.
- 3) Screening Questionnaire for TMS Candidates; screens for TMS contraindications and will be administered in an interview format with both the child and parent present.
- 4) TMS Adverse Effects Questionnaire (AEQ) is a 13-item questionnaire completed by patient (items 1-10) and clinician (items 11-13).
- 5) The SST is a well-validated computerized task measuring RI. The SST is a visual choice reaction time task in which participants watch arrows (left or right) on the screen and respond by pressing the appropriate button. In a randomly assigned proportion of trials, an audible signal is heard after presentation of the arrow, and subjects are instructed to inhibit the motor response (button press). The inter-stimulus interval and stop-signal delay are varied according to individual performance so that each person can successfully inhibit responses to 50% of stop trials. SSRT (time required to inhibit a prepotent motor response) is calculated from these data. Successful stop trials (i.e., those in which a motor response is successfully inhibited) are most relevant for understanding functional neural correlates of RI, and will be of primary interest in EEG analyses (see below).
- 6) EMA will be used to obtain youth ratings on three items (modified from NIMH rating scales) assessing obsessions, compulsions, and mood on a 7-point scale (1 = not at all to 7 = very much). These items have shown differential change with frequent assessment post-TMS for adults with OCD and have been used in EMA studies of OCD. Youth will receive a text message prompt every two hours (between 9am and 9pm) over the two days following the clinical interview and each study visit (6 days total). The text prompt will include a redcap link for completing EMA items. Similar EMA items and procedures have been used successfully with adolescents of diverse backgrounds in a large number of studies to date.

**7). HARM Form.** At visits 1 and 2, we will administer the HARM form to assess for new or worsening suicidal or homicidal ideation (SI or HI). The Harm Form was developed for SI/HI monitoring by the Child and Adolescent Multimodal treatment Study (CAMS) team^105 and NIMH program staff and was also used in the POTS II and POTS Jr trials for youth with OCD. The form is designed to ascertain the presence of any thoughts, wishes, or behaviors related to self-harm or harm to others since the last study contact. This brief measure consists of two broad initial probes—one asking about self-harm and the other about harm to others—and 5-8 contingent follow-up questions assessing acute risk status.

#### **EEG procedures:**

**EEG Acquisition.** EEG will be recorded continuously (band pass 0.1 - 100 Hz; sampling rate 10000 Hz) from the scalp using Brainvision system with the actiCAP slim 64 channel cap with a nose reference, along with additional electrodes to record the vertical and horizontal electrooculogram (EOG). All electrode impedances will be maintained below 10 kΩ.

**EEG Data processing.** EEG pre-processing: EEG recordings will be band-pass filtered between 1 and 55 Hz and visually inspected to remove segments with extreme motion artifacts. Noisy channels and dead channels will be removed, and the missing channels interpolated. To correct for eye-related artifacts (saccades and blinks), temporal independent component analysis will be performed. The components that have a correlation higher than 0.8 with the EOG electrodes will be removed, and the remaining components will be added together to restore the EEG signal without the artifacts. The cleaned EEG will be segmented into epochs consisting of the time period during auditory stimulus presentation, along with a 100 ms baseline and a 500 ms offset period. Epochs with a voltage greater than  $\pm 100 \mu\text{V}$  will be considered an artifact, and if the artifact cannot be corrected, will be excluded from the analysis. All EEG data preprocessing will be performed using the software package MNE-python. Variable calculation. P3 is a well-established correlate of RI performance on the SST (including SSRT) and of activation in inhibitory networks. We will calculate P3 amplitude on successful stop trials by averaging the epochs of successful stop trials time-locked to the stop signal from the midline electrode (Cz).

#### **Randomization:**

The order in which participants receive TMS and Sham (visit 1 or 2) will be randomly assigned (blocking on medication status, biological sex, and baseline CYBOCS severity) and masked for all study staff except for the statistician.

[figure not shown]

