**Masking** procedures will be implemented to control for expectancy effects related to TMS stimulation. Persons who will be masked to TMS status are: participants; parents (if applicable), study staff administering clinical assessments, SST, and EEG, study staff administering TMS, and all study investigators except for the study statistician responsible for randomization. Forms assessing masking adequacy will be given to participants, parents, and staff administering TMS. Study staff administering TMS will remain masked using the following procedures. The Sham and Active Coils are identical in appearance. The motor threshold coil which will be used for all procedures is different in appearance than the active and sham treatment coils. Each coil will each be labeled with a unique random number (e.g. 1639 vs 2740) but the technician will not know which is active and which is sham. The Neuromodulation Facility Manager will hold the masking log in a secure location. A masked TMS coil assignment log (included in CRF) will be used for the study with consecutively consented subjects assigned to consecutive ID#s that appear in the form. For each ID# there will be a coil number (e.g., 1639 or 2730) assigned in random order prior to start of the study. At the time of each treatment, the technician will confirm the participant's name and consult this form to select the correct coil to attach for the treatment session that day. The date of each session must be documented, along with the maximum intensity (relative to MT) applied in the session that day,etc.

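### Treatment order is blocked on three baseline factors in one section but taken from a pre-filled, consent-order list in another, so the counterbalancing is not guaranteed as written

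*Combined protocol and SAP*

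**What the plan says.** Four places in the combined protocol and SAP bear on how a participant's order is set.

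- **Study Design** describes a "within-subject, counterbalanced design comparing TMS vs Sham in a brief 2-visit protocol enrolling 14 youth".
- **Randomization** assigns the order at random, "blocking on medication status, biological sex, and baseline CYBOCS severity". It gives no block size, CY-BOCS cut-point, or rule that equal numbers receive each order.
- **TMS Protocol, Masking paragraph** describes the form the technician uses to pick the coil. It has "consecutively consented subjects assigned to consecutive ID#s that appear in the form". Of its contents it says "For each ID# there will be a coil number", "assigned in random order prior to start of the study".
- **Study Procedures** lists, for the clinical interview, informed consent, then "child assent, and assessment of inclusion/exclusion criteria". The CY-BOCS is part of that assessment, and the same interview settles final eligibility.

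The models in Description of the Statistical Methods test visit type (TMS or Sham) by timing (pre or post). They name no visit-number, sequence or blocking-factor term.

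**The concern.** The coil log determines the order actually delivered. If it is one list filled before anyone is enrolled and used in order of consent, a participant's line cannot depend on medication, sex or severity. Severity is not even known when consent is signed. The blocking in the Randomization section then cannot be carried out through the log as described.

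A second problem follows from the timing. If an ID is issued at consent and the participant then fails eligibility, that line is spent. A list built with equal halves can lose its balance in this way.

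At stake is the split of orders. Each participant receives both conditions, so medication, sex and severity cancel as main effects in the within-person contrast. What does not cancel under an unequal split is a difference between visit 1 and visit 2, and the planned models have no term to absorb it.

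**Working it through.** The plan gives no figure for order balance, so there is none to reproduce. The inputs from the documents are 14 enrolled (Study Design), 10 analysable (Sample size and power), three blocking factors (Randomization), and one ID series in consent order (Masking). Number of strata, block size, list restriction and number of screen failures are not stated; the values below are assumptions.

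**1. The texts side by side.** Blocking needs the factor values before a line is drawn. The log draws the line at consent. The CY-BOCS comes after consent. All three hold together only with stratum-specific lists or ID ranges issued after assessment, which the visible text does not describe.

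**2. Order split among 14.**

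- *Unrestricted list:* P(7:7) = C(14,7)/2^14 = 3432/16384 = 20.9%. P(8:6 either way) = 2 × 3003/16384 = 36.7%. So 9:5 or worse = 42.4%.
- *Stratified blocks:* three two-level factors make 8 cells, or 14/8 = 1.75 participants per cell. The results come from simulation with 40,000 runs per setting. As a check for blocks of 2, the expected number of cells with an odd count is 8 × (1 − 0.75^14)/2 = 3.93, which is the variance of the difference in numbers between orders. Its square root, 1.98, agrees with the simulated SD of 1.98.
- *List forced to equal halves, IDs issued at consent:* with 20 consented and 6 failing, P(7:7) = C(10,7)²/C(20,14) = 14400/38760 = 37.2%. P(8:6) = 2 × 45 × 210/38760 = 48.8%, which leaves 14.1%. Other counts follow in the same way.

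| Procedure (assumed detail) | 7:7 | 9:5 or worse |
|---|---|---|
| Unrestricted list | 21% | 42% |
| 8 equal strata, blocks of 2 | 40% | 11% |
| 8 equal strata, blocks of 4 | 30% | 25% |
| 12 strata, blocks of 2 | 33% | 19% |
| Equal-halves list, no screen failures | 100% | 0% |
| Equal-halves list, 16 consented | 53% | 0% |
| Equal-halves list, 18 consented | 42% | 8% |
| Equal-halves list, 20 consented | 37% | 14% |

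**3. Effect of a given split.** Let a visit effect shift the TMS minus Sham difference by +π in one order and −π in the other. The unadjusted mean then carries |n1 − n2|/N of π. Adjusting for visit removes this and multiplies the variance by N²/(4·n1·n2).

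| Split | Share of visit effect carried | Variance factor if adjusted |
|---|---|---|
| 8:6 | 2/14 = 14% | 196/192 = 1.02 |
| 9:5 | 4/14 = 29% | 196/180 = 1.09 |
| 10:4 | 6/14 = 43% | 196/160 = 1.23 |

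**4. Which visit effect.** P3 and SSRT are measured before and after stimulation at each visit, so π is a visit effect on the pre-to-post change only. EMA is collected after the interview and after each visit. Visit 2 has no pre-rating period of its own, so drift over time enters the comparison more directly.

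**5. After attrition.** Start at 7:7 and lose 4 at random, unrelated to order. Then 5:5 has probability 441/1001 = 44%, 6:4 has 490/1001 = 49%, and 7:3 has 70/1001 = 7%. Under unrestricted allocation, 7:3 or worse among 10 has probability 352/1024 = 34%. At 7:3 the share carried is 4/10 = 40% and the variance factor is 100/84 = 1.19.

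**The case against.** The strongest reply is that this is a gap in description rather than a faulty design. Stratum-specific lists or ID ranges would reconcile the two sections. A figure is missing beside the Randomization text, and the log itself sits in a case report form that is not shown. That stands against the inference, which a reader might draw, that the two procedures are irreconcilable. They conflict as worded, and wording can resolve it.

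A reader might also infer that neither procedure can deliver counterbalancing. The documents do not support this. Small blocks keep the split within 8:6 in about 89% of runs, against 58% for an unrestricted list, and an equal-halves list gives 7:7 if every ID goes to an eligible participant. A random order also does not rule out a restricted one.

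A third tempting inference is that ordinary practice from visit 1 to visit 2 biases P3 and SSRT. It does not: each visit's own pre-stimulation measurement removes a stable shift in level. Under random order, what remains is chance imbalance given the realised split, and the documents give no size for any visit effect.

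Three further points stand in part.

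- Phone screening and record review precede consent, so six later failures may be too many; with two, 9:5 cannot occur.
- An exact 7:7 start still ends at 5:5 in only 44% of cases once 4 of 14 are lost. A balanced list is therefore not enough without a visit term.
- The single coil number per ID may be loose wording. The technician consults the form for each session, and with two coils the first code implies the second.

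None of this explains how an ID issued at consent could reflect a CY-BOCS score not yet obtained.

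**Conclusion.** The concern holds in a limited form. As written, the blocking cannot be carried out through the described log, and screen failures after consent could undo any balance in it. The counterbalancing is therefore not guaranteed. That rests on the text alone.

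The size is illustrative. The chance of 9:5 or worse ranges from 0% to 42% across the settings tabulated above, depending on strata, block size, list restriction and screen failures that the plan does not state. At 9:5, an unadjusted analysis carries 29% of a visit effect on the pre-to-post change (P3, SSRT), or of drift between the post-visit rating periods (EMA compulsions). Whether that is material depends on a visit effect the documents do not quantify.

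The documents do not show actual bias, confounding of treatment with the three factors, or that blocking must be abandoned. Blocking on prognostic factors is a legitimate choice. The difficulty is three factors at once in 14 participants, with no stated constraint on the overall split. The correction is cheap and should be made before the log is issued.

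**What to change.** 1. Issue the allocation line only after eligibility and the baseline CY-BOCS are complete.
2. Use a list restricted to equal numbers per order (7 TMS-first, 7 Sham-first). It can be unstratified. If the sponsor keeps blocking, use at most one binary factor, or minimisation, and constrain the overall order split as well.
3. Record a visit-1 and a visit-2 coil code for each ID.
4. Reword the Randomization section and the Masking paragraph so that they describe the same procedure.
5. Add a visit (period) term and its interaction with timing to the models for Aims 2 and 3. The interaction is what adjusts the visit type by timing contrast, and it handles the imbalance that attrition leaves.

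The cost is protocol wording, a regenerated coil log, and possible chance imbalance of any dropped factor between the two orders, which matters little for a within-person contrast unless visit effects differ by that factor. The visit term costs about 2% in variance at 8:6 and 9% at 9:5, and nothing at an equal split apart from the degree of freedom used.
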